- Estimates of whole blood and serum cobalt and chromium metal ion levels for subjects implanted with the WMT MoM THA System overall and for each defined cross-section interval. Here, we will also categorize patients enrolling only one hip and patients enrolling both hips, and estimates of whole blood and serum cobalt and chromium metal ion levels by this classification will be obtained as well.
- An estimate of baseline whole blood and serum cobalt and chromium metal ion levels subjects not previously implanted with metal implants (Group-2 subjects) compared to subjects previously implanted with metal implants (Group-1 subjects).
- Full descriptions of functional outcomes, as assessed by HOOS scores, of subjects implanted with the WMT MoM THA System overall and for each defined crosssection interval in subjects with and without ALTR (Group-1 subjects).
- A comparison of cobalt and chromium metal ion levels in subjects with and without confirmed ALTR (Group-1 subjects).

E. Follow-Up Time Points

Follow-up for **Group 1** will consist of a single study visit (Visit 1) in which they will be evaluated with a functional assessment (HOOS Score), an Environmental Assessment, past medical history, whole blood and serum cobalt, and chromium metal ion levels and MARS MRI. Group-1 subjects who are diagnosed with ALTR will be required to complete a 1-year follow-up visit (Visit 2) or until they are revised, whichever comes first. Therefore, they will be followed for 1-year or until any revision surgery at which point the subject will be taken off study.

Follow-up for **Group 2** will consist of a single study visit (Visit 1) in which they will be evaluated with an Environmental Assessment, past medical history, and whole blood and serum cobalt and chromium metal ion levels. The subjects will be taken off study immediately after this single visit.

F. Study Duration

The total study duration from final approval of the study protocol until the submission of the final report is expected to be 42 months.

G. Duration of Subject Participation

The duration of subject participation will be limited to a single study visit with multiple study activities (Visit 1). If all activities cannot be completed during the single visit due to scheduling logistics, subjects may have up to 4 weeks to complete the remaining activities.

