The Interim Data Looks will be provided to FDA beginning six months after the final protocol is approved and every six months for the first two years. Interim reporting will be provided annually beginning Year 3 until study completion.

A final study report will be provided to FDA following study completion and final data analysis.

XII. SUBJECT SELECTION

A. Inclusion Criteria

To be included in **Group 1**, subjects must meet all of the following criteria:

- 1. Has been implanted with appropriate components of the WMT MOM THA System for at least four years +/- six months (i.e. 3.5 years since implantation), but not longer than eight years and six months (i.e. 8.5 years since implantation)
- 2. Has previously undergone primary THA for any of the following:
 - a. non-inflammatory degenerative joint disease including osteoarthritis, traumatic arthritis, or avascular necrosis:
 - b. inflammatory degenerative joint disease including rheumatoid arthritis;
 - c. correction of functional deformity.
- 3. Is willing and able to complete required study visit(s) and assessments
- 4. Plans to be available for the required study visit
- Is capable of providing sufficient blood for sampling according to blood draw procedures
- 6. Is willing to sign the approved Informed Consent document

Previously implanted bilateral subjects can have both THAs enrolled in the study provided: 1) the specified combination of components were implanted in both, 2) all other aspects of the Inclusion/Exclusion Criteria are satisfied, 3) enrollment does not

exceed the subject count specified in the Clinical Trial Agreement and protocol enrollment strategy, and 4) the subject agrees to a second Informed Consent document and data collection specific to the second THA. Enrollment and treatment of a previously unimplanted hip is not permitted in this study.

To be included in **Group 2**, subjects must meet all of the following criteria:

- 1. Does not have a metal implant (total hip, total knee, spinal, etc.) with the exception of dental implants
- 2. Is not an employee of the Investigator
- 3. Is willing and able to provide Informed Consent document
- 4. Is willing and able to attend the requested study visit
- Is capable of providing sufficient blood for sampling according to blood draw procedures

B. Exclusion Criteria

Subjects will be excluded from either study group if they meet any of the following criteria:

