- 1. Subject is currently enrolled in another clinical investigation which could affect the endpoints of this protocol
- 2. Subject is unwilling or unable to sign the Informed Consent document
- 3. Subject has documented substance abuse issues
- 4. Subject has an emotional or neurological condition that would pre-empt their ability or willingness to participate in the study
- 5. Subject is currently incarcerated or has impending incarceration
- 6. **Group 1 only:** Subject has a condition or previously implanted medical device that contraindicates MRI (e.g. pacemaker, implantable defibrillator)
- 7. **Group 1 only:** Subject was skeletally immature (less than 21 years of age at time of plantation)

C. Point of Enrollment

Subjects will be considered enrolled in the study when they have been informed of all aspects of the study, had ample time to review the Informed Consent document, signed the Informed Consent document, and satisfied the Inclusion/Exclusion Criteria.

D. Subject Withdrawal or Discontinuation

Subjects maintain the right to discontinue their participation in the study at any point. If a subject exercises this right, the Investigator will make every effort to ascertain and document the reason for withdrawal.

E. Subjects Lost to Follow-Up

If a subject is not able to complete the study after being enrolled, the Investigator will document the last contact with the subject. This is only for subjects in Group-1. All attempts to contact the subject will be documented in the source documentation.

XIII. PROCEDURES

A. Enrollment Procedures

As the subject enrollment will be carried out in at least 5 sites, the enrollment of subjects will be done according to the following criteria within each site:

• Enrollment will start with Group-1 subjects.

 After enrolling the first Group-1 subject, if there is a Group-2 candidate available then he/she can be enrolled if he/she

- o meets the Inclusion/Exclusion Criteria, and
- o is ±10 years of the previously enrolled Group-1 subject, and
- same gender of the previously enrolled Group-1 subject.
- Each site should alternate enrollment between Group-1 and Group-2 as described above. This will generate a more balanced age and gender distribution.
- Group-1 enrollment will not be limited due to lack of eligible Group-2 subjects.
- Each site can continue enrolling to Group-1 and Group-2 until the enrollment targets are reached for each cross-sectioned year and for Group-2, or until instructed by MPO.

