Group 1: Investigators will attempt to identify potential subjects from those they have previously implanted at their individual practices. Investigators will review their records for consecutive subjects starting with those implanted closest to 8 years from the protocol approval date with the study components and moving forward in time. The Investigator should not skip any potential subject implanted with the appropriate combination of components. Potential subjects will be cross-sectioned using the methods described above. The Investigator should attempt to contact any previously implanted subject that satisfies the Inclusion/Exclusion Criteria until there is a total of 35 subjects enrolled collectively at all sites for each year window (+ 6 months).

Please note: previously implanted subjects with a pending revision of the WMT MoM components are eligible for enrollment and will need to be screened.

If a subject has appropriate WMT MoM components implanted in both hips, both can be enrolled in the study, as long as both hips satisfy the Inclusion/Exclusion Criteria. Subjects will be asked to sign two consent forms and complete two sets of questionnaires, one for each hip, but have only one blood draw and one MRI, if sufficient. Each THA will be assigned to the appropriate cross-sectioning interval (e.g. the two THAs may be in different intervals if bilateral THAs were not performed simultaneously).

Group 2 (Control Subjects): Investigators will attempt to identify potential control subjects from their individual practices as long as the subjects satisfy the Inclusion/Exclusion Criteria. Each subject can only be enrolled one time (see above for Group-2 enrollment guidelines).

Group 1 & 2: The Investigator will inform potential subjects of all aspects of the study, including all potential risks and benefits. Potential subjects will be allowed ample time to consider and ask questions about the information they have been provided. If after being informed the potential subject still wishes to participate, they will be asked to sign an Informed Consent document. Once the subject has signed the Informed Consent document and has met the Inclusion/Exclusion Criteria, they will be considered enrolled in the study. Any subject who signs the Informed Consent document and fails to satisfy the Inclusion/Exclusion Criteria will be considered a screen failure. Screen failures will be captured in the electronic data capture (EDC) system.

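### Group 1 ion levels are split by hips enrolled, not implants present, and only controls are barred from other metal, so the one-hip level and any excess attributed to the device can be overstated by an unknown amount

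*Protocol*

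**What the plan says.** **The split.** Protocol section X.D (Secondary Endpoints) plans ion levels overall and by cross-section interval, and adds: "we will also categorize patients enrolling only one hip and patients enrolling both hips". It continues: "estimates of whole blood and serum cobalt and chromium metal ion levels by this classification will be obtained as well".

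**When a second hip is enrolled.** Section XIII.A (Enrollment Procedures) permits but does not require it: "If a subject has appropriate WMT MoM components implanted in both hips, both can be enrolled in the study". Section XII.A sets conditions. One is that "the specified combination of components were implanted in both"; another is that "the subject agrees to a second Informed Consent document and data collection specific to the second THA". Enrolment limits must not be exceeded, and each hip must lie within 3.5 to 8.5 years of implantation. Section X.B has sites told when a yearly window is full, and XIII.A foresees a patient's two hips falling in different windows.

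**One blood sample per patient.** Under XIII.A and XIII.D a patient with both hips enrolled has a single draw. Section X.B analyses patient-level data by patient.

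**Other metal.** A Group 2 subject must meet this criterion (XII.A): "Does not have a metal implant (total hip, total knee, spinal, etc.) with the exception of dental implants". Group 1 has no matching rule. The only exclusion in XII.B that touches other implants is: "Subject has a condition or previously implanted medical device that contraindicates MRI (e.g. pacemaker, implantable defibrillator".

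**Data on other implants.** Section XIII.B collects the status of other joints affecting ambulation (Group 1 only), medical history and an environmental metal-ion form. It takes the Group 1 history and demographic data from the time of the primary hip operation.

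**The concern.** A blood ion level belongs to the whole patient. The protocol treats it so: it uses one draw for two hips and keeps metal implants out of the control group. Whether a hip is enrolled is an administrative fact. A split by number of hips is informative about ions only if it counts the hips that are there.

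Two distinct problems follow.

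1. **Label.** A patient whose second MoM hip is not enrolled is counted as one-hip, although the blood reflects two. This affects the one-hip estimate and anyone's reading of it against the two-hip estimate.
2. **Eligibility asymmetry.** Knee, spinal or other hip metal is possible in Group 1 and barred in Group 2. If the difference between groups is read as the contribution of the study hip system, it may include other metal.

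The study answers a regulator's concern about high cobalt and chromium concentrations with these devices (section V), so attribution of the ion results matters.

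**Working it through.** **Step 1. Can a patient with two MoM hips be classed as one-hip?** Yes, by any of four routes in the text: the second hip has components outside the study system; it lies outside 3.5–8.5 years; its window or the site's allotment is full; or the patient declines the second consent. None of these removes that hip's contribution to the blood sample.

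**Step 2. Can Group 1 carry other metal?** Yes. The Group 1 inclusion list and the exclusion list contain no bar on another hip, a knee or spinal hardware unless it contraindicates MRI. Matching of controls covers age and gender only (X.B, XIII.A).

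**Step 3. The plan's own scale.** The protocol gives no figure for this bias. It does give detectable differences in standard deviation (SD) units (X.B): 0.65 per cross-section year and 0.4 overall, at 90% power and 5% type I error. Taking a two-sided test and every hip as a separate patient:

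- 35 vs 100: (1.960 + 1.282) × √(1/35 + 1/100) = 0.637 SD; power at 0.65 SD is 0.911.
- 155 vs 100: (1.960 + 1.282) × √(1/155 + 1/100) = 0.416 SD, which rounds to the stated 0.4; power at exactly 0.4 SD is 0.877.

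These figures only supply a scale. A bias from uncounted implants does not shrink as the sample grows.

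**Step 4. Size of the bias.** Let d be the excess over controls from one study hip. Let a fraction f of one-hip patients carry another cobalt/chromium source that adds r×d. Neither f nor r is in the documents; both are assumed.

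- One-hip excess: (1 − f)d + f(1 + r)d = (1 + f×r)d.
- If the two-hip class has excess 2d and no other source, two-hip minus one-hip: 2d − (1 + f×r)d = (1 − f×r)d.

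| f | r | One-hip excess × | Two-minus-one × | True 0.40 SD reads as | True 0.65 SD reads as |
|---|---|---|---|---|---|
| 5% | 0.1 | 1.005 | 0.995 | 0.402 | 0.653 |
| 20% | 0.5 | 1.10 | 0.90 | 0.44 | 0.715 |
| 20% | 1 | 1.20 | 0.80 | 0.48 | 0.78 |
| 40% | 1 | 1.40 | 0.60 | 0.56 | 0.91 |

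The SD columns apply the one-hip multiplier to a Group 1 versus Group 2 difference in which each Group 1 patient has one study hip. If a share b has both hips enrolled, the study hips contribute (1 + b)d on average. With f now the share of all Group 1 patients, the multiplier is 1 + f×r/(1 + b). With b = 20% (assumed), f = 20% and r = 0.5 it is 1 + 0.10/1.20 = 1.083.

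**Step 5. Could the collected data repair this later?** Perhaps not. Section XIII.B dates the Group 1 history to the primary operation, 3.5 to 8.5 years before the draw. Section X.E lists past medical history at Visit 1, but nothing shown asks for an inventory of current implants.

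**The case against.** The strongest case against has several parts.

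- **The label cannot bias the group comparison.** The Group 1 versus Group 2 difference pools all Group 1 patients, whatever their class. This stands. A reader might infer that the enrolled-hip split inflates that difference; it does not. Only the eligibility asymmetry bears on it.
- **The comparison is what the protocol says it is.** X.D sets people without metal implants against people with them, and a surveillance study of consecutive patients will naturally include other implants. This stands too. The difference is biased only when read as the effect of the study hip system. That reading is natural, because the objective in IX.B is framed around patients implanted with that system.
- **A reader might infer that the estimates are inflated, or by some fixed percentage such as 10–30%.** The documents do not support this. They give no prevalence of other implants, and such a range requires every extra implant to add as much as a study hip (r = 1). Only cobalt and chromium are measured, so an implant that releases neither has r = 0.
- **No formal one-versus-two comparison is planned.** Correct: X.D asks for separate estimates. Dilution matters only to someone who compares them. It also depends on the source lying in the one-hip class alone, as an unenrolled second MoM hip does; knee or spinal metal equally common in both classes would not shrink the gap.
- **The data may already be collected, and sensitivity analyses belong in the SAP.** The case report forms and SAP are not shown, so a gap in them cannot be asserted. But the protocol itself fixes the classification, and no SAP can use a current-implant variable that was never recorded.

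**Conclusion.** The point holds in limited form. The rule in X.D can place patients with two MoM hips in the one-hip class, so that estimate can be too high by an unknown amount, and an informal reading against the two-hip estimate is then diluted. Separately, the unequal rules on other metal mean that the Group 1 versus Group 2 difference can overstate the excess if it is attributed to the study hip system.

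An uncounted cobalt/chromium source can only add, so the direction of the first effect is clear. The size is not: the 0.5% to 40% range rests wholly on assumed f (5–40%) and r (0.1–1), with additive excesses. If no Group 1 patient carries another such source, there is no bias. The point concerns secondary ion endpoints only; the incidence of adverse local tissue reactions is untouched.

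**What to change.** In X.D, replace the enrolled-hip split with mutually exclusive classes by implants in situ at the Visit 1 blood draw, regardless of enrolment and ignoring dental implants as for controls:

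- (a) one study MoM hip and no other metal implant;
- (b) two MoM hips and no other metal implant;
- (c) any study hip plus any other metal implant.

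To keep the classes from overlapping, state that an unenrolled or other-maker MoM hip on the second side counts towards (b), and that other metal in (c) means anything beyond the MoM hips already counted.

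Add a record of current metal implants at Visit 1, dated to the draw; the joint-status item in XIII.B is not enough while its source is the time of the primary operation. Report the Group 1 versus Group 2 comparison for class (a) alongside the planned all-Group 1 comparison.

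The cost is one case report form item, relabelled tables, and lower precision in class (a), which will be smaller than Group 1. No eligibility rule or enrolment target changes.

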- Vomiting
- Hyperventilation

Adverse events associated with MRI include:

- Malfunctioning of heart pacemakers, defibrillation devices and cochlear implants
- Reaction to contrast media.

IX. STUDY OBJECTIVES

A. Primary Objective

The primary objective of the study is to determine the incidence of adverse local tissue reactions (ALTR) in each THA implanted with the WMT MoM THA System overall and for yearly cross-section intervals from 4-year to 8-year post implant.

B. Secondary Objective

The secondary objectives include:

- To determine whole blood and serum cobalt and chromium metal ion levels for subjects implanted with the WMT MoM THA System overall and for each defined cross-section interval
- To estimate baseline whole blood and serum and serum cobalt and chromium metal ion levels for subjects not implanted with any metal implants, and compare the cobalt and chromium metal ion levels between the implanted subjects and controls (Group-1 vs. Group-2 subjects).
- To compare functional outcomes, as assessed by HOOS score (Hip disability and Osteoarthritis Outcome Score), of subjects implanted with the WMT MoM THA System overall and for each defined cross-section interval in subjects with and without ALTR (Group-1 subjects).
- To compare cobalt and chromium metal ion levels in subjects with and without confirmed ALTR (Group-1 subjects).

X. STUDY DESIGN

A. Study Design

This is a cross-sectional, multi-center study to evaluate outcomes in subjects previously implanted for between 4 and 8 years prior to the study start date. A target of 5 sites, with up to 7 sites total, will participate in this study. Subjects will be identified from Investigator records. Collected data will be evaluated in aggregate and cross-sectioned by year of implantation according to the time that has elapsed between implantation.

B. Sample Size and Subject Cross-Sectioning

There will be two groups of subjects in this clinical study: **Group 1** will consist of subjects previously implanted with the WMT MoM THA System; **Group 2** (i.e., Control Group) will consist of control subjects not implanted with any other metallic devices (excluding dental implants).

The sample size for **Group 1** is 155 THAs that must have been implanted between 4 and 8 years prior to enrolling in this study. This sample size will allow for 35 THAs to be included at each 1-year interval between Years 5 and 8 and 15 THAs to be included in the Year 4 interval (Table 4).

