For each cross-section year, a sample size of 35 hips will give us a two-sided 95% confidence interval for the incidence rate of ALTR with a width no greater than 0.346. With the entire Group-1 cohort (n=155), the width of such a confidence interval will be no wider than 0.163.

The sample size for **Group 2** is 100 control subjects.

Subjects will be identified from Investigator records. Collected data will be evaluated in aggregate and cross-sectioned by year of implantation. Subjects will be cross-sectioned

by the time that has elapsed between implantation and the initial visit (e.g. 4 years, 5 years) using contiguous visit windows (number of years + 6 months).

As subject enrollment will be carried out in at least 5 sites, enrollment will begin with Group-1. Group-2 subjects will be matched by age and gender to Group-1 to achieve a more balanced distribution between the two groups. To minimize the potential of overenrollment, the study team will generate enrollment summaries and inform the sites if enrollment targets are reached for any given cross-sectioned year or for Group-2.

Table 4. Group 1 enrollment stratification based on time lapse from MoM THA implantation date to initial study visit.

Group 1	Year 4 + 6m	Year 5 + 6m	Year 6 + 6m	Year 7 + 6m	Year 8 + 6m
N (hips)	15	35	35	35	35

In comparing metal-ion levels between Group-1 and Group-2, we will have 90% power to detect a 0.65 standard-deviation unit difference as significant with 5% Type-1 error rate in each cross-sectioned year assuming that the ion levels in Group-1 and Group-2 will have similar variability. With the comparison of the entire Group-1 with Group-2, we can detect 0.4 standard-deviation unit difference as significant with 90% power and 5% Type-1 error rate.

Due to potentially enrolling both hips of a given patient, whenever data is collected for the patient, not for each hip, the data analysis for that particular study objective will be carried out at the patient level. If the data is collected for each hip for a given study objective, the data analysis will be carried out for each hip assuming that the hips are independent.

C. Primary Endpoint

The primary endpoint is an estimate of the incidence of ALTR in each THA implanted with the WMT MoM THA System overall and for each yearly defined cross-section interval.

D. Secondary Endpoints

The secondary endpoints include:

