At screening, the subject will be assigned a seven digit subject identification number. The first three digits will be the code assigned to the Investigation Site. The second

three digits will correspond to the order the subject was enrolled (i.e. the first subject enrolled at each site will be 001). The last digit will be an "L" or "R" corresponding to the left or right hip. Control subjects will have a "C" assigned as the last digit (instead of "L" or "R"). This seven digit code will be used to identify the subject in the EDC.

B. Subject Medical History, Concomitant Medications, and Demographics (Both Groups 1 and 2)

Subject medical history and demographic information will be collected from the medical record **in both groups.** Data will come from the time of the primary THA surgery and recorded for **Group 1** subjects. **Group 2** data will come from the current medical records. The following information will be collected on these forms:

- Date of birth
- Gender
- Height
- Weight
- Status of other joints that affect ambulation (Group 1 only)
- Past medical events including significant diagnoses and major medical events and/or THA related Serious Adverse Events (SAEs)
- Concomitant medications

An Environmental (Metal Ion) Assessment form will also be completed by subjects in both Groups 1 and 2 to document environmental exposure to metal ions. Bilateral subjects with both THAs enrolled will be asked to complete one Environmental Assessment form which will be entered into the database for both enrolled THAs.

C. Operative Events (Group 1 only)

All of the following Operative information will be collected for all subjects in **Group 1**. Bilateral subjects with both THAs enrolled will have operative information completed separately for each THA.

i. Primary THA Procedure Information (Group 1 only)

The following information related to the subject's primary THA operation will be obtained from the medical record and recorded for all subjects in **Group 1**.

- Date of admission
- Primary diagnosis for index THA procedure
- Previous treatments of the operated hip (osteotomy, resection, fracture fixation, or fusion)
- Date of operation
- Operative side
- Cement usage
- Bone graft usage
- Intraoperative complications
- Date of discharge

ii. Device Information (Group 1 only)

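### Group 1 weight, medical history, other-joint status and medications are dated to the hip operation 3.5 to 8.5 years before the blood draw, while Group 2 values are current

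*Protocol*

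**What the plan says.** Section XIII.B takes medical history and demographic information from the medical record in both groups but gives each group its own reference date. For Group 1: "Data will come from the time of the primary THA surgery and recorded for" Group 1 subjects. For Group 2: "data will come from the current medical records". The forms cover date of birth, gender, height, weight, past medical events, concomitant medications and, in Group 1 only, the status of other joints that affect walking.

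The outcomes carry a different date. Table 1 (section III) and section X.E place the blood draw, HOOS and MARS MRI at Visit 1. Section XII.A admits Group 1 hips from 3.5 to 8.5 years after implantation.

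Comparing cobalt and chromium between the groups is a secondary objective (section IX.B). On balance between the groups, section X.B says: "Group-2 subjects will be matched by age and gender to Group-1 to achieve a more balanced distribution between the two groups". Section XIII.A implements this as within 10 years of age and the same gender. One exposure instrument is common to both groups: "An Environmental (Metal Ion) Assessment form will also be completed by subjects in both Groups 1 and 2" (section XIII.B).

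**The concern.** A comparison of implanted and non-implanted subjects is observational. With matching on age and gender only, these forms are the main means in the protocol of showing that the groups are alike in other respects when blood is taken. As section XIII.B reads, Group 2 is described at about the time of sampling and Group 1 as it was years earlier. A diagnosis made or a drug started between the operation and Visit 1 would appear on a control's form but, unless it is THA-related, not on an implanted subject's.

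The lag also lengthens with the cross-section year, so covariates are most out of date in the oldest interval. A patient with staged bilateral implants has two index dates but one blood draw (sections XIII.A and XIII.D), and patient-level data are analysed per patient (section X.B). Such a patient could carry two differently dated sets of values, neither from the day of the draw.

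This is a collection rule. Group 1 attends once unless ALTR is diagnosed, so a later analysis plan cannot reliably recover values that were never recorded.

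**Working it through.** The plan gives no figure of its own for this point. The check is a reading of the text, followed by the size of the lag.

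**1. Reference dates side by side**

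| Item | Group 1 | Group 2 |
|---|---|---|
| Weight, past medical events, medications (XIII.B) | primary THA | current records |
| Other-joint status (XIII.B) | primary THA | not collected |
| Environmental Assessment (Tables 1 and 2) | Visit 1 | Visit 1 |
| Metal ions (Tables 1 and 2) | Visit 1 | Visit 1 |

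**2. Does another section collect current Group 1 values?** Table 1 lists the history, medication and demographic forms at Visit 1. That says when they are completed; XIII.B says what date the data refer to. Section XIV.E reaches back to implantation, but only for procedure-related SAEs and device effects. No section asks for Group 1 weight, medications or general diagnoses as of Visit 1.

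**3. Length of the lag.** The range is 3.5 to 8.5 years (section XII.A), plus up to 4 weeks if activities are spread out. With the Table 4 quotas (15 hips at Year 4; 35 each at Years 5 to 8):

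mean lag = [15×4 + 35×(5+6+7+8)] / 155 = (60 + 910) / 155 = 970 / 155 = 6.26 years.

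This is a mean over hips at the window midpoints. In Group 2 the lag is about 0.

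**4. Share of Group 1 with a changed status.** The documents give no rate of change. Assume a constant yearly probability r of at least one relevant change; the share is 1 − (1 − r)^6.26.

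- r = 2%: 1 − 0.98^6.26 = 0.12
- r = 5%: 1 − 0.95^6.26 = 0.27
- r = 10%: 1 − 0.90^6.26 = 0.48

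At r = 5% the share runs from 1 − 0.95^3.5 = 0.16 at the short end of the window to 1 − 0.95^8.5 = 0.35 at the long end.

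**5. What the mismatch does not reach.** The power statements in section X.B concern a difference of unadjusted means. Using power = Φ(d / √(1/n1 + 1/n2) − 1.96):

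- 35 versus 100 at d = 0.65: Φ(0.65/0.1964 − 1.96) = 0.91
- 155 versus 100 at d = 0.40: Φ(0.40/0.1283 − 1.96) = 0.88, which is the stated 90% only if 0.4 is a rounding of 0.416

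No covariate enters either calculation. Date of birth and gender do not depend on the source date, so the matching stands. Height is little affected.

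**The case against.** The strongest reply is that no analysis in the protocol uses these values. It names no adjusted ion model and no comparability table, and the metal-exposure form is completed at Visit 1 in both groups. That stands: the point concerns what a supporting table or adjustment could use, not the planned unadjusted comparison.

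The second reply is that XIII.B may be loosely worded for 'from surgery onward'. Its list includes THA-related SAEs, many of which would arise after surgery, and the draft case report forms (Appendix 3) are not shown. This has some force for THA-related events. It fits weight poorly, and section XIV.E spells out a running period where one is meant. If the text is only ambiguous, it still needs correcting across 5 to 7 sites.

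Third, index-surgery values are useful for describing patients at implantation. They are, which is why the fix keeps them.

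A reader might infer more than the documents support:

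- **That the ALTR versus no-ALTR comparisons are distorted in the same way.** Both arms are Group 1 and follow one rule, so there is no old-versus-current contrast between them. Their covariates are merely out of date at measurement.
- **That later implants are recorded in controls but missed in Group 1.** Section XII.A makes a control with any non-dental metal implant ineligible, so implants are screened out of Group 2, not recorded. XIII.B lists implants for neither group.
- **That Group 1 will certainly look healthier than it is, or that the ion difference is biased by a known amount.** Accrued diagnoses would tend to be undercounted, but the direction for weight and medications is uncertain. The documents link none of these items quantitatively to cobalt or chromium.

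**Conclusion.** The point holds as a mismatch in data collection. Section XIII.B dates Group 1 weight, medical history, other-joint status and medications 3.5 to 8.5 years before the blood draw (mean about 6.3 years on the quotas) and dates the Group 2 values to the present. Any comparability table or adjustment built on them would compare unlike times.

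The lag follows from the documents. The share of subjects affected does not: the 12% to 48% range rests wholly on assumed yearly rates of 2% to 10%, and no bias in the ion difference can be derived from it. The primary ALTR incidence, the unadjusted ion comparison and its power, the matching and the Environmental Assessment are untouched. This is a cheap improvement to the credibility of a secondary comparison, not a flaw that invalidates a planned analysis.

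**What to change.** Amend XIII.B so that weight, current diagnoses and concomitant medications are recorded as of Visit 1 in both groups. For Group 1, also record as of Visit 1 the status of other joints and any other metal implants present. The implant item is an addition: Group 1 has no implant exclusion beyond MRI contraindication, whereas controls are screened for implants.

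Keep the index-surgery values as separate, dated Group 1 fields. State that Visit 1 values are used in group comparisons and any adjustment, and reconcile XIII.B with Table 1. A patient with two enrolled hips then has one set of values dated to the single blood draw.

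The cost is protocol and case report form wording, the FDA and IRB/EC approvals that section XV requires for an amendment, and a few minutes per Group 1 subject at a visit already scheduled. Subjects who have already completed Visit 1 would need their values taken from records near that date, with the source marked.
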